16.6 Monitoring

By signing this protocol, the Investigator grants permission to the Sponsor (or designee), and appropriate regulatory authorities to conduct on-site monitoring and/or auditing of all appropriate study documentation.

16.7 Subject Confidentiality

In order to maintain subject confidentiality, only a site number, subject number, subject initials (US sites only) and subject's CFF patient registry number (US sites only) will identify all study subjects on CRFs and other documentation submitted to the Sponsor. Additional subject confidentiality issues (if applicable) are covered in the Clinical Study Agreement.

17 ADMINISTRATIVE, ETHICAL, REGULATORY CONSIDERATIONS

The study will be conducted according to the Declaration of Helsinki, Protection of Human Volunteers (21 CFR 50), Institutional Review Boards (21 CFR 56), and Obligations of Clinical Investigators (21 CFR 312).

To maintain confidentiality, all laboratory specimens, evaluation forms, reports and other records will be identified by a coded number and initials only. Clinical information will not be released without written permission of the subject, except as necessary for monitoring by the FDA. The Investigator must also comply with all applicable privacy regulations (e.g., Health Insurance Portability and Accountability Act of 1996).

17.1 Protocol Amendments

Any amendment to the protocol will be written by the Sponsor. Protocol amendments cannot be implemented without prior written IRB/IEC approval except as necessary to eliminate immediate safety hazards to patients. A protocol amendment intended to eliminate an apparent immediate hazard to patients may be implemented immediately, provided the IRBs/IECs are notified within five working days.

17.2 Institutional Review Boards

The protocol and consent form will be reviewed and approved by the IRB/IEC of each participating center prior to study initiation. SAEs regardless of causality will be reported to the IRB/IEC in accordance with the standard operating procedures and policies of the IRB/IEC, and the Investigator will keep the IRB/IEC informed as to the progress of the study. The Investigator will obtain assurance of IRB/IEC compliance with regulations.

Any documents that the IRB/IEC may need to fulfill its responsibilities (such as protocol, protocol amendments, consent forms, information concerning patient recruitment, payment or compensation procedures, or other pertinent information) will be submitted to the IRB/IEC. The IRB/IEC's written unconditional approval of the study protocol and the informed consent form will be in the possession of the Investigator before the study is initiated. The IRB/IEC's unconditional approval statement will be transmitted by the Investigator to the Sponsor or

designee prior to the shipment of study supplies to the site. This approval must refer to the study by exact protocol title and number and should identify the documents reviewed and the date of review.

Protocol and/or informed consent modifications or changes may not be initiated without prior written IRB/IEC approval except when necessary to eliminate immediate hazards to the patients or when the change(s) involves only logistical or administrative aspects of the study. Such modifications will be submitted to the IRB/IEC and written verification that the modification was submitted and subsequently approved should be obtained.

The IRB/IEC must be informed of revisions to other documents originally submitted for review; serious and/or unexpected adverse experiences occurring during the study in accordance with the standard operating procedures and policies of the IRB/IEC; new information that may affect adversely the safety of the patients of the conduct of the study; an annual update and/or request for re-approval; and when the study has been completed.

17.3 Informed Consent Form

Informed consent will be obtained in accordance with the Declaration of Helsinki, ICH GCP, US Code of Federal Regulations for Protection of Human Subjects (21 CFR 50.25[a,b], CFR 50.27, and CFR Part 56, Subpart A), the Health Insurance Portability and Accountability Act (HIPAA, if applicable), and local regulations.

The Investigator will prepare the informed consent form, assent (if applicable) and HIPAA authorization (if applicable) and provide the documents to the Sponsor or designee for approval prior to submission to the IRB/IEC. The consent form generated by the Investigator must be acceptable to the Sponsor and be approved by the IRB/IEC. The written consent document will embody the elements of informed consent as described in the International Conference on Harmonisation and will also comply with local regulations. The Investigator will send an IRB-approved copy of the Informed Consent Form to the Sponsor (or designee) for the study file.

A properly executed, written, informed consent will be obtained from each subject prior to entering the subject into the trial. Information should be given in both oral and written form and subjects must be given ample opportunity to inquire about details of the study. If appropriate and required by the local IRB/IEC, assent from the subject will also be obtained. If a subject is unable to sign the informed consent form and the HIPAA authorization, a legal representative may sign for the subject. A copy of the signed consent form (and assent) will be given to the subject of the subject and the original will be maintained with the subject's records.

During the course of the study, if modifications are made to the consent form that impact the subject, the subject will be re-consented as described above.

17.4 Consent for Collection and Use of CFF Registry ID Number (US Sites Only)

To facilitate future evaluation of retrospective and prospective information from all patients who screen for this study, the subject's CFF Registry ID number will be collected. The CFFNPR collects data on all CF patients who consented to participate in the CFFNPR and who are followed at CFF-accredited care centers. The registry data includes information from clinical encounters, hospitalizations courses of antibiotics, and year-end surveys. Data also include microbiology results, spirometry results, CF genotype and other information such as survival.

17.5 Publications

The preparation and submittal for publication of manuscripts containing the study results shall be in accordance with a process determined by mutual written agreement among the study Sponsor and participating institutions. The publication or presentation of any study results shall comply with all applicable privacy laws, including, but not limited to, the Health Insurance Portability and Accountability Act of 1996.

17.6 Investigator Responsibilities

By signing the Agreement of Investigator form, the Investigator agrees to:

1. Conduct the study in accordance with the protocol and only make changes after notifying the Sponsor (or designee), except when to protect the safety, rights or welfare of subjects.
2. Personally conduct or supervise the study (or investigation).
3. Ensure that the requirements relating to obtaining informed consent and IRB/IEC review and approval meet federal guidelines, as stated in § 21 CFR, parts 50 and 56.
4. Report to the Sponsor or designee any AEs that occur in the course of the study, in accordance with §21 CFR 312.64.
5. Ensure that all associates, colleagues and employees assisting in the conduct of the study are informed about their obligations in meeting the above commitments.
6. Maintain adequate and accurate records in accordance with §21 CFR 312.62 and to make those records available for inspection with the Sponsor (or designee).
7. Ensure that an IRB/IEC that complies with the requirements of §21 CFR part 56 will be responsible for initial and continuing review and approval of the clinical study.
8. Promptly report to the IRB/IEC and the Sponsor (or designee) all changes in the research activity and all unanticipated problems involving risks to subjects or others (to include amendments).
9. Seek IRB/IEC approval before any changes are made in the research study, except when necessary to eliminate hazards to the patients/subjects.
10. Comply with all other requirements regarding the obligations of clinical investigators and all other pertinent requirements listed in § 21 CFR part 312.

19 APPENDIX 1. SCHEDULE OF EVENTS

	Visit 1	Visit 2	Visit 3 ¹
Event/Assessment	Day 1 ⁴	Between Day 7 - 10 of IV Antibiotics (±1 days)	Between Day 24 - 35 2 wks after scheduled completion of IV treatment (+/-2 days)
Informed Consent	X		
Medical History, Demographics, CF Diagnosis, CF Registry ID	X		
Collect subject health care resource use	X ²	X ³	X ³
Concomitant Medication Review	X	X	X
Collect results of clinical care respiratory cultures for microbiology	X	➔	➔
Collect results of clinical care BUN, creatinine and serum glucose	X	➔	➔
Subject Questionnaire: CRISS	X	X	
Subject Questionnaire: CFRSD			X
Subject Questionnaire: EQ-5D-5L	X	X	X
Complete Physical Exam	X		
Abbreviated Physical Exam		X	X
Height	X		
Weight	X	X	X
Spirometry	X	X	X
Collect sputum for microbiome	X	X	X
Collect blood and test for CRP at site	X	X	X
Collect blood and freeze serum for banking	X	X	X
Complete Signs and Symptoms Assessment	X		
Allocation to group and Randomization to IV treatment duration		X	
Adverse Event Review		X	X

¹ Visit day will vary, dependent on group and duration arm

² Subject and care-giver job classifications

³ Subject-reported travel time to visits, IV treatment times, caregiver care times, additional clinic visits. At Visit 3, only Health Care Resource Use information that was not previously collected or has changed since data was collected at Visit 2 will be collected.

⁴ Day 1 is defined as the day that IV antibiotics are initiated. Visit 1 may occur up to three days prior to the initiation of IV antibiotics or up to 1 calendar day after IV antibiotics are initiated.

1.1 Study Rationale and Design

In patients with cystic fibrosis (CF) who are experiencing a pulmonary exacerbation, a strong desire among clinicians to reduce treatment durations (and reduce cost, inconvenience, and potential toxicities) is in conflict with belief that patients not responding robustly to treatment might benefit from extending treatment. An assessment taken after one week of treatment has been demonstrated to predict the overall response, especially for those with an early robust improvement (Early Robust Response; ERR). These patients are often treated with shorter courses of intravenous (IV) antibiotics in clinical practice and will likely experience no additional benefit from an extended IV treatment (although this has never been objectively studied). Patients who have a less robust early response to treatment often receive extended treatments in a belief that better overall responses are attained. Although the additional clinical benefit of prolonged courses of IV antibiotics should outweigh potential risks of toxicity, treatment burden, and increased resource utilization, these relationships have also never been objectively tested.

This randomized, controlled, open-label study is designed to evaluate the efficacy and safety of differing durations of IV treatment, given in the hospital or at home, for a pulmonary exacerbation in adult patients with CF. The study will assess the non-inferiority of 10 days versus 14 days of treatment among ERR subjects and the superiority of 21 days versus 14 days treatment duration among the subjects who do not meet the ERR definition (non-ERR; NERR).

Subjects will undergo pulmonary function testing (spirometry) and complete a respiratory symptom score [Chronic Respiratory Infection Symptom Score (CRISS)] at initiation of IV treatment (Baseline/ Visit 1) and at Day 7-10 (Visit 2). At Visit 2, subjects will be allocated to groups ERR or NERR based on their initial clinical response as determined by their change in forced expiratory volume in 1 second (FEV₁; percent of predicted) and CRISS from Baseline and then subsequently randomized to an IV treatment duration (nested within group).

ERR subjects [$\geq 8\%$ predicted improvement in FEV₁ from Baseline (Visit 1) to Visit 2 and CRISS reduction of ≥ 11 points from Baseline (Visit 1) to Visit 2] will be randomized 1:1 to either 10 days or 14 days total IV antibiotic treatment duration. Remaining (NERR) subjects will be randomized 1:1 to receive either 14 or 21 days total IV antibiotic treatment duration. All subjects will be evaluated again at Visit 3, 14 days following scheduled completion of IV antibiotic treatment. Dependent on the treatment arm, subjects will be on study from 24 to 35 days.

The primary objective of this study is to evaluate the efficacy and safety of differing durations of IV antibiotic treatment for CF pulmonary exacerbations.

ERR Group: To determine if 10 days of IV antibiotic treatment (ERR-10) is as safe as and not clinically inferior (in terms of lung function response) to 14 days of IV antibiotic treatment (ERR-14) among subjects meeting the ERR threshold at Visit 2.

NERR Group: To determine if 21 days of IV antibiotic treatment (NERR-21) is clinically superior (in terms of lung function response) and safe, compared to 14 days of IV antibiotic treatment (NERR-14) among subjects not meeting the ERR threshold at Visit 2.

The secondary objectives are to:

- Evaluate efficacy of differing IV antibiotic treatment durations on other clinical outcomes such as weight, respiratory symptoms, and subsequent IV antibiotic treatments for pulmonary exacerbation.

- Determine the feasibility, uptake and adherence to a standardized protocol of antibiotic selection.

Other objectives are to:

- Provide a study platform for ancillary studies of PEx treatment in adults with CF, including investigations into respiratory microbiome, health economics, and systemic inflammation.
- Establish a biorepository of CF serum and sputum samples before, during and after treatment for an adult PEx for use by the CF research community. Interim DSMB Reviews

1.2 Data Monitoring Committee Reviews

Oversight for this trial will be performed by the Cystic Fibrosis Foundation (CFF) Data Safety Monitoring Board (DSMB; Chair, [name]). A Data Monitoring Committee (DMC) has been selected by the Associate Chair [name] to specifically monitor this trial according to the DMC Charter. The DMC consists of at least two physicians experienced in treating patients with CF and a biostatistician. The DMC is responsible for safeguarding the interests of study participants, assessing the safety and efficacy of study procedures, and for monitoring the overall conduct of the study.

The Table below outlines reporting schedule, content, and participation throughout the study.

Content of Reporting	Semi-Annual (no meeting)	Initial 10% Enrollment (teleconference)	Initial 20% Enrollment (as needed) (teleconference)	Comprehensive 50% Enrollment (teleconference)	Comprehensive 75% Enrollment (teleconference)
Enrollment/Feasibility (Pooled)	--	--	--	O	O
Enrollment/Feasibility (by Duration Arm)	C	O	O	C	C
Abbreviated Safety Summaries (by Duration Arm)	C	C	C	C	C
Comprehensive Efficacy Interim (by Duration Arm)	--	--	--	C	C

O - OPEN report for DMC, Study Biostatisticians, Study manager, and Sponsor-Investigators

C - CLOSED report for DMC and Study Biostatisticians only

Abbreviated summary reports tabulating SAEs by treatment duration arm will be reported to the DSMB on semi-annual basis starting after the first patient is randomized. There will be one initial interim report at approximately 10% of enrollment, followed by a second identical report at 20% of enrollment, if deemed necessary. The initial interim report will focus on feasibility, adherence to protocol, return for randomization, and adherence to randomized treatment duration arm. An unblinded, open review by treatment duration arm with the DMC and the Sponsor-Investigators of Sections 1-3 and Appendix A of this document will take place. The safety data summarized by treatment duration group will be presented in the closed section of the DMC meeting (Sections 4-5), as outlined in the table above.

Comprehensive interim reports including efficacy endpoints and formal statistical monitoring will be generated after approximately 50% and 75% of subjects have been randomized. The contents of these reports are outlined in the table above and will be comprised of both an open (pooled enrollment) and a closed report (feasibility, safety, and efficacy by treatment duration arm).

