15 STATISTICAL METHODS AND CONSIDERATIONS

A detailed Statistical Analysis Plan (SAP) will be written that will describe all analyses that will be generated for this study. All analyses will be performed using SAS[®] (SAS Institute, Inc., Cary, NC, USA) or R (R Foundation for Statistical Computing, Vienna, Austria). The SAP will contain any modifications to the analysis plan described below.

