15.6 Interim Analysis

A pre-defined monitoring plan for feasibility, variance estimation, sample size adaptation, and study stopping rules will be formalized in conjunction with the DMC and will be in place prior to initiating the study. Feasibility will be closely monitored for the first 100 enrolled patients to ensure adherence to protocol, return for randomization, and adherence to randomized treatment duration arm.

Each treatment group (ERR and NERR) will have separate monitoring criteria and a decision to stop one may not be conditional on the other.

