15.7 Sample Size

ERR Group:

A non-inferiority design to show that the change in FEV₁ between Visit 1 and Visit 3 in the ERR subjects who received 10 days of treatment (ERR-10) is no more than 3.5 % predicted less than ERR subjects who received 14 days treatment (ERR-14) requires 310 subjects (155 per arm) who complete the study. STOP pilot data indicate a mean change (SD) in FEV₁ between baseline and Day 28 in patients with an early response to be 12.5 % predicted, 95% CI [9.5, 15.6]. Assuming two-sided alpha =0.05, standard deviation =9.0% predicted and the true difference between two groups is zero, the ERR study has 93% power to detect a 3.5 % non-inferiority margin which preserves 72% of the treatment effect or 63% of the lower bound of treatment effect observed in the STOP pilot.

NERR Group:

A superiority design to show that the change in FEV₁ between Visit 1 and Visit 3 in NERR subjects who received 21 days treatment (NERR-21) is at least 2.5 % predicted greater than NERR subjects who received 14 days treatment (NERR-14) requires 570 subjects (285 per arm) who complete the study. STOP pilot data indicate a mean change (SD) in FEV₁ between baseline and Day 28 in patients without an early response to be 4.0 % predicted, 95% CI [1.9, 6.1]. Assuming two-sided alpha =0.05 and standard deviation =9.0% predicted, the NERR study has 91% power to detect a 2.5% or greater increase in FEV₁ among those treated with 21 days compared to 14 day IV antibiotic. A 2.5% improvement was chosen to represent a minimal clinically important difference in lung function to justify the additional burden and potential toxicity of 21 days of treatment versus 14. It is important to note that statistical significance can be shown at the end of the superiority NERR study with a smaller treatment effect than 2.5%.

Observed treatment effect (mean difference in absolute FEV₁ change) and the 95% CI will provide primary inference and evidence of non-inferiority, superiority, or lack thereof in both the ERR and NERR groups. Motivated to ensure conclusive results, this study was designed to provide sufficiently narrow 95% CIs at the end of the trial (ERR 95% CI half-width=2%;

NERR 95% CI half-width=1.5% when both SD=9%).

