1.3 Report Generation

The final statistical report will describe and justify any deviations from the original statistical plan described herein. Analyses will be performed using SAS 9.4 software or most current version of R. No adjustments for multiple comparisons will be made. Any analyses requiring CFFNPR data will be performed after the study close-out. The timing of these analyses will depend on availability of the Registry data containing relevant study participant information. Any tables or figures requiring such data are noted with an asterisk in the table and figure shells that follow. All programs used to produce this report will be documented, tested, and archived and all tables, figures and listings will be validated before considered final.

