2.5 Summary of Primary Efficacy Endpoint

The primary endpoint is the absolute change in percent predicted FEV₁ from Visit 1 (Baseline) to two weeks after scheduled completion of IV antibiotics (Visit 3). The primary endpoint is compared between treatment durations within ERR and NERR groups using Analysis of Variance (ANOVA) adjusted for dichotomous randomization strata: Visit 1 FEV₁, number of IV-treated exacerbations in prior year, location of IV administration by Visit 2, and use of systemic corticosteroids by Visit 2. The treatment effect for each group (ERR and NERR) (estimated via adjusted ANOVA least squares means) is presented along with corresponding 95% confidence intervals. Observed treatment effect and the 95% CI provide primary inference and evidence of non-inferiority, superiority, or lack thereof in both the ERR and NERR groups.

ERR Group (PP population): The non-inferiority of ERR-10 versus ERR-14 is tested against a 3.5 % predicted non-inferiority margin with a one-sided 0.025 level of significance.

NERR Group (ITT population): The superiority of NERR-21 versus NERR-14 is tested with a two-sided 0.05 level of significance.

The primary analysis for ERR is repeated in the ITT population, and the primary analysis for NERR is repeated in the PP population.

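### Do the planned efficacy looks at about 50% and 75% undermine the full-alpha final tests in SAP 2.5?

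*SAP*

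**What the plan says.** SAP 1.2 has the DMC monitor the trial under a DMC Charter and schedules two comprehensive reviews: "Comprehensive interim reports including efficacy endpoints and formal statistical monitoring will be generated after approximately 50% and 75% of subjects have been randomized". The efficacy part is by duration arm and closed, seen only by the DMC and the study biostatisticians.

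Protocol 15.6 puts the rules elsewhere: "A pre-defined monitoring plan for feasibility, variance estimation, sample size adaptation, and study stopping rules will be formalized in conjunction with the DMC". It adds that each group "will have separate monitoring criteria and a decision to stop one may not be conditional on the other". Protocol 14 refers the reader to 15.6, the Charter and the SAP for the timing and content of interim reviews.

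For the final analysis, SAP 2.5 states: "The superiority of NERR-21 versus NERR-14 is tested with a two-sided 0.05 level of significance". ERR is tested against its "non-inferiority margin with a one-sided 0.025 level of significance". The treatment effect with its 95% CI is the primary inference in both groups. SAP 1.3 adds: "No adjustments for multiple comparisons will be made".

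Protocol 15 promises that "A detailed Statistical Analysis Plan (SAP) will be written that will describe all analyses that will be generated for this study". Protocol 15.7 gives 93% power for ERR (155 completers per arm, margin 3.5, SD 9) and 91% for NERR (285 per arm, difference 2.5, SD 9). It also says: "Motivated to ensure conclusive results, this study was designed to provide sufficiently narrow 95% CIs at the end of the trial", with half-widths of 2% and 1.5%.

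**The concern.** Two formal looks at by-arm efficacy, followed by a final test at the full level with no adjustment mentioned, is the usual pattern of uncontrolled repeated testing. If a group can be declared successful at 50% or 75% and is otherwise tested at 1.96, there are three chances to reject and the overall error exceeds 5%.

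The estimate is also at stake, because SAP 2.5 rests its inference on the effect and its CI. A group stopped early would have a wider interval than the full-enrolment design, and the estimate at the stop would on average be too large. For NERR this matters because Protocol 15.7 names 2.5 points as the minimal clinically important difference. A reader holding only the SAP cannot tell which situation applies.

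**Working it through.** **Inputs.** From Protocol 15.7: n = 155 and 285 per arm, SD 9, ERR margin 3.5 with true difference 0, NERR difference 2.5. From SAP 1.2: looks at 50% and 75%. From SAP 2.5: the final levels. The documents give no boundary, so the boundaries below are assumptions. So are the information fractions of 0.50, 0.75 and 1.00 of 310 and 570 completers.

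**Step 1: reproduce the stated power and half-widths.** Drift = difference / (9 × √(2/n)), and power = Φ(drift − 1.96).

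- ERR: 3.5 / (9 × √(2/155)) = 3.424, power 92.8% (stated 93%).
- NERR: 2.5 / (9 × √(2/285)) = 3.316, power 91.2% (stated 91%).
- Half-width 1.96 × 9 × √(2/n): 2.00 and 1.48 (stated 2% and 1.5%).

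**Step 2: overall error if a look may stop a group for benefit and 1.96 is kept at the end.** The Z statistics are jointly normal with correlation √(tᵢ/tⱼ).

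| Assumed interim rule | Two-sided error | Final \|Z\| that holds 5% | Power ERR / NERR with that value |
|---|---|---|---|
| No stop for efficacy or non-inferiority | 5.00% | 1.960 | 92.8% / 91.2% |
| \|Z\| > 3.29 | 5.02% | 1.962 | 92.8% / 91.2% |
| \|Z\| > 3 | 5.09% | 1.968 | 92.8% / 91.2% |
| Lan-DeMets O'Brien-Fleming (2.963, 2.359) | 5.54% | 2.014 | 92.4% / 90.8% |
| Lan-DeMets Pocock (2.157, 2.312) | 7.2% | 2.327 | 88.9% / 86.8% |
| Each look at nominal 0.05 | 9.7% | not applicable | not applicable |

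For the three conservative rules, the one-sided ERR errors are 2.51%, 2.55% and 2.77%.

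**Step 3: can the stated figures show which rule applies?** Final half-widths with each rule's own critical value (ERR / NERR) are:

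- unadjusted: 2.004 / 1.478
- |Z| > 3.29: 2.006 / 1.479
- |Z| > 3: 2.012 / 1.484
- O'Brien-Fleming: 2.06 / 1.52

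All are close to 2% and 1.5%. Power does not separate the single-look design from the two |Z| rules either. The stated figures therefore do not identify the rule.

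**Step 4: effect of a stop on the interval and the estimate.** Half-width 1.96 × 9 × √(2/(n·t)) at 50% and 75% is 2.83 and 2.31 for ERR, and 2.09 and 1.71 for NERR.

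For NERR with true difference 2.5, under the three conservative rules:

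- The mean estimate among early-stopped trials is 3.10 (O'Brien-Fleming, 70% stop early), 3.46 (|Z| > 3, 47%) or 3.65 (|Z| > 3.29, 36%).
- Among trials that continue, it is 1.75 to 2.13.
- Over all trials, it is about 2.67 to 2.70.

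For ERR with true difference 0, the overall mean is about +0.24 to +0.28. Coverage of the ordinary 95% CI is 94.8% to 95.0% at these true values. It is 94.5% for NERR at zero difference under O'Brien-Fleming.

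**The case for a change.** The strongest case is that the Charter cannot fully answer the point, because the final level and CI are written in the SAP and their validity depends on the monitoring rule. Protocol 14 names the SAP as one place for interim-review details, and Protocol 15 says it covers all analyses. SAP 1.2 gives timing, content and access but not the stopping direction. Protocol 15.6 lists stopping rules separately from variance estimation and sample-size adaptation, so they are more than the blinded variance check in 15.7. The trial is also open-label, which makes a traceable rule more valuable.

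It stands that one sentence in the SAP would spare the reader a search. It also stands that the 50% and 75% are not tied to a per-group total: 1236 × 0.96 split 1:2 gives about 396 ERR and 791 NERR completers, against stated minimums of 310 and 570.

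The claim that the plan is wrong as written does not stand. SAP 1.2 names the Charter, and Protocol 15.6 assigns stopping rules to a pre-defined plan with separate criteria per group, so the reader is told where the rule belongs. SAP 1.3 speaks of multiple comparisons and does not mention repeated looks. The half-widths are design figures for the end of the trial and promise nothing for a group stopped early. Overestimation at an early stop is a general property of group-sequential designs and would remain with a fully specified boundary.

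**Conclusion.** No change to the plan is needed. This is missing detail that analysts fill sensibly. The study biostatisticians receive the closed reports, so they can be expected to know the boundary. If it carries a final critical value other than 1.96, they would use it, and SAP 1.3 requires the final report to describe and justify any departure from the plan.

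The size depends on a rule that the documents reviewed do not show. There is no inflation if the looks cannot stop a group for efficacy or non-inferiority. With conservative boundaries and 1.96 kept at the end, the excess is 0.02 to about 0.5 percentage points of two-sided error, and the matching final level costs less than half a point of power. Only a Pocock-type or unadjusted rule combined with an uncorrected final test would make the problem material (7.2% or 9.7%). Nothing in either document suggests such a rule, and formal monitoring under a pre-agreed plan makes it unlikely.

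This conclusion assumes that the Charter and monitoring plan hold the stopping rules as Protocol 15.6 says, and that the looks fall near 0.50 and 0.75 of each group's information.
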